6.1 Eligibility Criteria

6.1.1 Inclusion Criteria

- Adult patients (age ≥ 18) with type 1 diabetes diagnosis and a duration of diabetes of at least 10 years
- Gold score < 4
- HbA1c $\geq 6.5\%$ within the last 3 months or at screen visit
- Stable insulin regimen (MDI or insulin pump) for at least 3 months, as deemed stable by principal investigator
- Depression/anxiety medications stable for at least 3 months
- Ability and willingness to wear CGM continuously during study participation
- Participants must use their own smartphone, and have the ability and willingness to use CGM smartphone applications compatible with their smartphone
- Ability and willingness to check SMBG using own supplies, as instructed by study staff
- Ability and willingness to document when having symptoms of hypoglycemia in the CGM smartphone app or in a diary
- If using insulin pump, willing to operate insulin pump without threshold suspend feature or hybrid closed-loop, if applicable
- Proficient in speaking, reading and understanding English in order to complete surveys and testing of cognitive function
- Women of child-bearing age must agree to procure and use contraception throughout the study

6.1.2 Exclusion Criteria

A subject will not be included for consideration in this study if any of the following criteria are met:

- Pregnancy or planning pregnancy
- eGFR ≤ 30 mL/min per 1.73 m², if available from medical record
- Currently participating in a research study or completed any other research study within 6 months of screening date
- Current or recent use within 3 months of an insulin delivery system that adjusts insulin in response to continuous glucose monitoring (CGM) data (such as an automated insulin delivery system like hybrid closed-loop insulin pump therapy)
- Known dementia or mild cognitive impairment diagnosis
- Diabetic ketoacidosis within the last 6 months
- Use of non-insulin medications to treat diabetes
- Those planning to change diet or exercise regimen during the study
- History of trans-sphenoidal surgery or surgery to the upper part of the nasal cavity, chronic sinusitis, severe deviated septum, or difficulty with smell and/or taste
- Severe psychiatric illness
- Allergy to adhesives, insulin or any components of insulin product
- Subject cannot adequately demonstrate ability to use and deploy the devices as determined by investigator

- Evidence of suicidality using the Columbia-Suicide Severity Rating Scale (C-SSRS)
- Subject has history of any of the following: moderate to severe pulmonary disease, poorly controlled congestive heart failure, significant cardiovascular and/or cerebrovascular events within previous 6 months, condition known to affect absorption, distribution, metabolism, or excretion of drugs such as any hepatic, renal or gastrointestinal disease or any other clinically relevant abnormality or illness that inclusion would pose a safety risk to the subject as determined by investigator.

7 Study Assessments and Procedures

A summary of study events and procedures is outlined in the Study Visit Table (see appendix 5). Demographic and Baseline Assessments

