5.1 Drug Administration Training

All subjects will receive training at start of treatment visits regarding home administration of IN insulin using the SipNose device during visits 2 and 7. Subjects will be required to administer the dose twice daily, one in the morning and the other in the evening (at least 8 hours between doses). If the SipNose device is discharged prior to insertion into the nose, then a retrial admission would be indicated. However, if the device is discharged following nasal insertion, then a retrial would not be permitted. The steps to ensure that subjects maintain compliance with the study protocol over 4 weeks include conducting the following:

- In-clinic training sessions: baseline/randomization (Visit 2) and start of treatment period 2 (visit 7)
- Phone call from study coordinator/investigator 1 day and 5 days after baseline visit and after Visit 7.

[figure not shown]

Figure 4: Study Design Flow Diagram

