5.2 Drug Administration with SipNose

Each dosing administration will require the following items: a) 2 SipNose Devices (2) 2 nose piece covers; b) device holder; c) study drug vial (10 ml vial of regular Insulin (Humulin-R or Placebo)); d) Insulin syringe; e) alcohol wipe; f) needle clipper and/or sharps container.

[figure not shown]

Figure 5: SipNose Device -Sp1N1C1

During the baseline/randomization visit the subject will administer the study drug in front of study personnel to ensure adherence to study protocol for drug administration. To ensure safety and medication compliance, subjects will be followed-up with a routine phone call 1 day and 5 days after baseline/randomization visit, 1 day and 5 days after Visit 7 (start of treatment period 2) and 1 week after final treatment visit.

Devices will be shipped to the clinical study site. One device with a nose piece cover will be supplied for each dose to be administered in the study. Devices are one-time use only. A kit containing all necessary items will be distributed to each subject and replaced at each study visit or as necessary. This will include several extra devices in case there are issues with any devices. Each device is to be loaded with a 10 unit dose of study drug to be used immediately or up to a maximum of 10 minutes prior to IN administration. The Nose Piece and Secondary Drug Container (temporary) are the only components of the device that will come into contact with the study drug and subject's nasal cavity.

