7.1.1 Visit 1: Screening (Day -14 to -7)

The following procedures will be performed at this visit:

- Obtain written informed consent from subject prior to any study related procedures
- Obtain Gold score – if <4, can stop here.
- Review inclusion/exclusion criteria
- Review medical history, as it pertains to inclusion/exclusion criteria
- Obtain subject's demographic information (date of birth, gender, race, education, etc.)
- Obtain details of medications, prescription, over the counter and vitamin/nutraceuticals taken over the course of the last 30 days prior to screening
- Collect vital signs (blood pressure & pulse), height, weight and BMI
- Obtain laboratory studies (Na, K, CO₂, Creat/GFR, AST/ALT, CBC w/ diff) and HbA1c POC, if not obtained within the past 3 months
- Urine pregnancy test in women of child bearing potential
- Perform a standard 12-lead ECG
- Download participant's blood glucose meter and/or CGM to evaluate recent glucose control
- Provide patients with glucagon self-injection kit, if they do not have a current kit at home
- Provider to see patient at this visit for visit assessment review

7.1.2 Visit 2: Randomization/Start of Treatment Period 1 (Day 0) - This will be scheduled as a morning appointment to accommodate visit length

The following procedures will be performed at this visit before SipNose administration:

- Assess for AE/SAEs
- Collect vital signs (blood pressure & pulse)
- CGM placed and started before testing (requires 2 hour warm up)
- Document BG values before and after cognitive testing
- C-SSRS questionnaire
- MNSI survey
- Hypo surveys (Clarke, HypoAQ)
- Cognitive tests (RBANS, Trail-making)
- Smell test (12-item UPSIT test versions A & B)
- Ensure patient still meets inclusion/exclusion criteria
- Randomize after completion of cognitive testing and hypo surveys
- SipNose device teaching

Administer first dose of intranasal insulin in clinic after above testing done, observe patient for 4 hours (only if randomized to intranasal insulin for treatment period 1).

The following procedures will be performed after the first dose is administered:

- Teach daily diary (or how to document within the Dexcom G6 app that symptomatic hypoglycemia is commencing)
- Teach glucagon and hypoglycemia management
- Teach CGM & apps (Including G6, Clarity, Follow apps); provide user guide materials
- Download participant's SMBG (if used) and/or CGM, and review for hypoglycemia and overall glucose control

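### As listed, Visit 2 confirms eligibility and randomizes before any SipNose teaching, so the device-ability exclusion is signed off without evidence and inability first shows once the sequence is known

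*Combined protocol and SAP*

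**What the plan says.** Section 6.1.2 lists as an exclusion: "Subject cannot adequately demonstrate ability to use and deploy the devices as determined by investigator". This is a judgement by the investigator, and it needs something to observe.

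Section 5.1 sets out when SipNose training takes place: "In-clinic training sessions: baseline/randomization (Visit 2) and start of treatment period 2 (visit 7". The screening list in 7.1.1 has no SipNose step.

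The Visit 2 list in 7.1.2 ends with these three items, in this order:

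1. "Ensure patient still meets inclusion/exclusion criteria"
2. "Randomize after completion of cognitive testing and hypo surveys"
3. "SipNose device teaching"

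The first dose follows. Section 5.2 adds: "During the baseline/randomization visit the subject will administer the study drug in front of study personnel". Because study drug is used, this demonstration also comes after assignment.

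Under 8.3 the investigators hold sealed envelopes with the insulin and saline sequence. No blinding is described in the protocol summary or in section 5.

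Section 12.1 promises an intention-to-treat analysis, and also says that subjects with missing data are left out. Section 12.4 bases 79.8% power on 10 subjects, 5 per sequence.

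**The concern.** An eligibility criterion should be settled before allocation. Here the listed order asks the site to confirm a criterion that nothing scheduled so far has tested for the SipNose. The relevant observation arrives minutes or hours later, when the envelope is open.

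The person who judges the criterion then knows the sequence. Visit 2 itself runs differently by assignment, since staff are to "observe patient for 4 hours (only if randomized to intranasal insulin for treatment period 1". Visit 7 (7.1.7) may be remote only for a saline start, which also requires staff to know the arm.

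Two things are at stake. A subject who fails and provides no CGM data is lost from a 10-person primary analysis and has used up a place in a permuted block. And a subjective decision to remove someone could be influenced by the known assignment.

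**Working it through.** **Order of events.**

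| Step | Where | Relative to randomization |
|---|---|---|
| Screening, no SipNose step | 7.1.1 | before |
| CGM placed and started | 7.1.2 | before |
| Cognitive tests and surveys | 7.1.2 | before |
| Eligibility re-check | 7.1.2 | before (as listed) |
| SipNose teaching | 7.1.2 | after (as listed) |
| Observed self-administration of study drug | 5.2 | after |

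On this order, no SipNose evidence exists at the eligibility check.

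**Inputs for the size.** From 12.4: margin 2%, root within mean square error 1.4%, true difference 0, 5 per sequence. From 12.2: two-sided 95% interval, equivalent to one-sided 0.025.

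**Formula.** For a 2x2 crossover with n1 and n2 per sequence:

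- SE = 1.4 × √(0.5 × (1/n1 + 1/n2))
- noncentrality = 2 / SE
- df = n1 + n2 − 2
- power = probability that a noncentral t variable exceeds the one-sided 0.025 critical value

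**The plan's own figure.** With 5+5: SE = 1.4 × √0.2 = 0.626, noncentrality 3.194, df 8, power 79.84%. This reproduces the stated 79.8%.

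**If losses are not replaced and leave no CGM data.**

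| Split | SE | Noncentrality | df | Power |
|---|---|---|---|---|
| 5+5 | 0.626 | 3.194 | 8 | 79.8% |
| 5+4 | 0.664 | 3.012 | 7 | 73.4% |
| 4+4 | 0.700 | 2.857 | 6 | 66.5% |
| 5+3 | 0.723 | 2.766 | 6 | 63.8% |

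**How likely is a loss?** The documents give no device-failure rate, so the following rates are assumptions. With rate p per subject, the chance of at least one failure among 10 is 1 − (1 − p)^10:

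- p = 2%: 18%
- p = 5%: 40%
- p = 10%: 65%

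The chance of two or more is 1.6%, 8.6% and 26.4% respectively.

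**A related inconsistency.** Section 5.2 has every subject dose in front of staff at the baseline visit. Section 7.1.2 states an in-clinic first dose only for those who start on insulin. If 7.1.2 governs, the two sequences do not get the same observed demonstration.

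**The case against.** The case on the other side is substantial and limits the point in several ways.

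- **Order.** A reader might infer that SipNose ability can be judged only after the envelope is opened. The text does not go that far. The Visit 2 items share one heading and are not declared sequential. At Visit 7 the SipNose teaching is listed among procedures after the first dose, so list order is not a strict guide. Nothing forbids earlier teaching, and the visit table in Appendix 5 is not in the text available. What stands is that the listed order is the only guidance a site has here, and it does not tie randomization to a demonstration.
- **CGM and apps.** A reader might extend the point to these, since "Teach CGM & apps (Including G6, Clarity, Follow apps); provide user guide materials" comes after the first dose. This does not hold. Section 7.1.2 has the CGM started before testing, and 5.4 describes starting it as including the app download and sensor insertion. That precedes randomization.
- **Removal after randomization.** No section says a randomized subject is removed under 6.1.2, which governs entry. Section 5.6 keeps subjects who discontinue treatment in follow-up where possible. Loss from the analysis would come through the missing-data rule in 12.1.
- **Accrual.** Consenting up to 20 to obtain 10 completers counts from consent and covers all losses, including screen failures. It is not evidence of device failure. It also leaves room to replace a loss, although no replacement rule is stated.
- **Likelihood.** Participants have had diabetes for at least 10 years and inject or use a pump. Known cognitive impairment is excluded, spare devices are supplied and training is repeated. Outright failure may be rare.
- **Bias.** Each participant is meant to receive both treatments through the same device, so losing someone does not deplete one treatment alone as it would in a parallel trial. No mechanism in the documents makes inability differ by sequence.

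**Conclusion.** The point holds for the SipNose. A site working through 7.1.2 as listed confirms the device-ability criterion before it has any evidence on it, and first sees inability with the sequence open to the investigator. The plan does not say what then happens to the subject.

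The consequence is mainly precision and sequence balance: power of about 73% after one loss (5+4) and about 64% after two from one sequence (5+3), against 79.8% planned. These figures assume that the lost subjects provide no usable CGM data and are not replaced, and that the other inputs in 12.4 are right. If losses are replaced, the power cost largely goes, but the block places are still used up. Exclusion made with the assignment in view is a risk, not a demonstrated bias, and the within-subject comparison limits it.

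This is a modest defect, worth correcting because the correction costs almost nothing in a 10-person trial.

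**What to change.** 1. In 7.1.2, move "SipNose device teaching" ahead of both "Ensure patient still meets inclusion/exclusion criteria" and "Randomize after completion of cognitive testing and hypo surveys". Add a return demonstration on a spare device, loaded and fired outside the nose. The 2-hour CGM warm-up offers time for it.
2. In 6.1.2, state that this criterion applies only before the envelope is opened. State that subjects with later device difficulty stay in follow-up under 5.6 and are analysed as randomized where CGM data exist. Reordering alone does not help a subject with no CGM data, so also say whether such a subject is replaced.
3. Reconcile 5.2 with 7.1.2 on whether every subject, or only those starting on insulin, takes the first dose in front of staff.
4. Check that Appendix 5 shows the same order.

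The cost is a rearrangement of existing Visit 2 steps and a few added sentences. A few spare devices and some teaching time will go to people who are then not randomized.

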7.1.1 Visit 1: Screening (Day -14 to -7)

The following procedures will be performed at this visit:

- Obtain written informed consent from subject prior to any study related procedures
- Obtain Gold score – if <4, can stop here.
- Review inclusion/exclusion criteria
- Review medical history, as it pertains to inclusion/exclusion criteria
- Obtain subject's demographic information (date of birth, gender, race, education, etc.)
- Obtain details of medications, prescription, over the counter and vitamin/nutraceuticals taken over the course of the last 30 days prior to screening
- Collect vital signs (blood pressure & pulse), height, weight and BMI
- Obtain laboratory studies (Na, K, CO₂, Creat/GFR, AST/ALT, CBC w/ diff) and HbA1c POC, if not obtained within the past 3 months
- Urine pregnancy test in women of child bearing potential
- Perform a standard 12-lead ECG
- Download participant's blood glucose meter and/or CGM to evaluate recent glucose control
- Provide patients with glucagon self-injection kit, if they do not have a current kit at home
- Provider to see patient at this visit for visit assessment review

7.1.2 Visit 2: Randomization/Start of Treatment Period 1 (Day 0) - This will be scheduled as a morning appointment to accommodate visit length

The following procedures will be performed at this visit before SipNose administration:

- Assess for AE/SAEs
- Collect vital signs (blood pressure & pulse)
- CGM placed and started before testing (requires 2 hour warm up)
- Document BG values before and after cognitive testing
- C-SSRS questionnaire
- MNSI survey
- Hypo surveys (Clarke, HypoAQ)
- Cognitive tests (RBANS, Trail-making)
- Smell test (12-item UPSIT test versions A & B)
- Ensure patient still meets inclusion/exclusion criteria
- Randomize after completion of cognitive testing and hypo surveys
- SipNose device teaching

Administer first dose of intranasal insulin in clinic after above testing done, observe patient for 4 hours (only if randomized to intranasal insulin for treatment period 1).

The following procedures will be performed after the first dose is administered:

- Teach daily diary (or how to document within the Dexcom G6 app that symptomatic hypoglycemia is commencing)
- Teach glucagon and hypoglycemia management
- Teach CGM & apps (Including G6, Clarity, Follow apps); provide user guide materials
- Download participant's SMBG (if used) and/or CGM, and review for hypoglycemia and overall glucose control
- Provider to see patient at this visit for visit assessment review
- Subject instructed to call if any hypoglycemia occurs before the next day phone call
- Subject instructed to return devices (used and unused) to study staff.

7.1.3 Phone Visit 3: Safety Check (visit 2 +1 day)

The following procedures will be performed at this visit:

- Study staff phone call to assess IN insulin compliance and AEs/SAEs
- Reinforce SipNose device training
- Reinforce daily diary training
- Review CGM data in Clarity

7.1.4 Phone Visit 4: Safety Check (Day 6 +/- 2 days)

The following procedures will be performed at this visit:

- Study staff phone call to assess IN insulin compliance and AEs/SAEs
- Reinforce SipNose device training
- Reinforce daily diary training
- Review CGM data in Clarity

7.1.5 Visit 5: End of Treatment Period 1 (Day 17 +/- 3 days)

The following procedures will be performed at this visit:

- Safety check and assess AEs/SAEs
- Gold score (for data collection purposes only)
- Medication review for any changes since screening
- VS (blood pressure/pulse)
- MNSI survey
- Hypo surveys
- Document BG values before and after cognitive testing
- Cognitive tests (study drug must have been taken prior to testing)
- Review daily diary
- Evaluate CGM for adequate data collected
- Inventory returned devices
- Download SMBG for safety, if used
- Download and review CGM data
- Provider to see patient at this visit for visit assessment review
- In the event the study site is recommending no non-essential in person clinic contacts (such as during the COVID-19 pandemic), this visit may be done remotely and study staff will obtain as much of the above procedural information as possible. Procedures such as MNSI survey and VS may not be able to be done.

7.1.6 Phone Visit 6: Safety Check 1 Week into the 2 Week Washout (Day 24 +/-2 days)

The following procedures will be performed at this visit:

- Study staff phone call to assess for AEs/SEs

7.1.7 Visit 7: Crossover/Start of Period Treatment 2 (Day 31 +/- 2 days)

The following procedures will be performed at this visit:

- Safety check and assess AEs/SAEs
- Medication review for any changes since screening

- Vital signs (blood pressure/pulse)

Administer first dose of intranasal insulin in clinic after above testing done, observe patient for 4 hours (only if randomized to intranasal insulin for treatment period 2).

The following procedures will be performed after the first dose is administered:

- SipNose device teaching
- Teach daily diary (or how to document within the G6 app that symptomatic hypoglycemia is commencing)
- Teach glucagon and hypoglycemia management
- Download SMBG for safety (if used)
- CGM placed
- Teach CGM & apps (Including G6, Clarity, Follow apps); provide user guide materials
- Provider to see patient at this visit for visit assessment review
- Subject instructed to call if any hypoglycemia before phone call occurs the next day
- In the event the study site is recommending no non-essential in person clinic contacts (such as during the COVID-19 pandemic), this visit may be done remotely and study staff will obtain as much of the above procedural information as possible, IF the participant is beginning the saline phase of the study only (not for insulin start). Distribution of supplies may be done remotely as well. If the participant is to begin the intranasal insulin part of the study, then the washout will be extended until a time when non-essential clinic visits at the site are permitted.

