2.2 Continuous Glucose Monitor (CGM) device

The commercially available Dexcom G6 CGM system (Figure 3) measures the glucose level in the interstitial fluid under the skin. The CGM system includes a sensor which has a small wire that is inserted under the skin, a transmitter that attaches to the sensor and a smartphone app that collects and displays the glucose results. The sensor will be placed under the skin and can stay in place for up to 10 days. The sensor will measure the glucose level in the interstitial fluid every five minutes and transmit that data to the smartphone. The screen will show in real-time the participant’s glucose value, most recent glucose trends, and an arrow indicating which way the glucose trend is predicted to go. Alarms can

be set to alert the participant to glucoses that are too high or too low, or if glucose trends are changing quickly. The data collected by the system can be downloaded and evaluated for several CGM-based metrics.

Figure 3: Dexcom G6 CGM System

3 Objectives

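### Visit 7 lists CGM placement after the first dose and Visit 2 lists it before, so the first 2 observed hours on insulin in Period 2 have no study CGM data; the effect on the primary endpoint is negligible

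*Combined protocol and SAP*

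**What the plan says.** Both start-of-period visits are divided by the first dose.

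- **Visit 2 (section 7.1.2).** The first list is headed "The following procedures will be performed at this visit before SipNose administration" and includes "CGM placed and started before testing (requires 2 hour warm up".
- **Visit 7 (section 7.1.7).** Only an adverse event check, a medication review and vital signs stand above the dose. For insulin starters the dose is given in clinic, with the instruction to "observe patient for 4 hours (only if randomized to intranasal insulin for treatment period 2". CGM placement comes in the next list, headed "The following procedures will be performed after the first dose is administered". Section 7.1.2 uses the same heading for its own post-dose list, but that list contains teaching and downloads, not sensor placement.
- **Sensor.** Section 5.4 gives a 2-hour warm-up before any glucose data are sent. Section 2.2 gives the sampling rate: "The sensor will measure the glucose level in the interstitial fluid every five minutes". Section 5 provides two 10-day sensors per period.
- **Meter glucose.** Visits 2, 5 and 10 carry the item "Document BG values before and after cognitive testing". Visit 7 has no cognitive testing and no such item. Its meter download retrieves existing readings and schedules none.
- **Endpoint.** Section 4.1 defines the primary endpoint as CGM percent time below 54 mg/dL. Section 11.6.1 says that non-severe hypoglycemia is not reported as an adverse event but will be captured in the data analysis.

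**The concern.** This is a safety trial with a CGM primary endpoint, and the protocol treats the first insulin dose as a moment that needs care. It requires 4 hours of observation, and during clinic restrictions it extends the washout rather than start insulin at a remote visit. If section 7.1.7 is followed literally, half of those observed hours have no study CGM data for everyone who starts insulin in Period 2. Non-severe lows in that window are not reported as adverse events, and the study sensor cannot record them. The CGM-based awareness measures in section 4.2 have no study-sensor data there either. Participants who start insulin in Period 1 have the sensor on before the dose, so CGM capture around the first insulin dose differs between the sequences.

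The point is limited to insulin starters. The text leaves unclear whether saline starters take their first Period 2 dose in clinic.

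**Working it through.** **The plan's own figures.** The 2% margin is 0.02 × 1,440 = 28.8 minutes per day, which agrees with the stated 30 minutes or so. The stated power also reproduces: standard error 1.4 × √(2/10) = 0.626, 8 degrees of freedom, one-sided 0.025 and true difference 0 give 79.84%, against 79.8% in section 12.4.

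**Can a Period 1 sensor still be running?** Two 10-day sensors worn from Day 0 end by about Day 20. The earliest Visit 7 is Day 31 − 2 = Day 29. That leaves at least 9 days with no study sensor, so none bridges the first Period 2 dose.

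**Size of the gap.**
- Share of observation: 2 h / 4 h = 50%, as a minimum, because placement follows the dose.
- Readings: 120 min / 5 min = 24 per participant. With 5 per sequence (section 12.4), 5 × 24 = 120. A full period has 288 per day × 14 to 20 days = 4,032 to 5,760 readings per participant.
- Doses: 2 per day × 14 to 20 days = 28 to 40 in a period. The gap follows one of them.

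**Share of the period, f.** Treatment lasts 14 to 20 days (section 5.6); nominal Period 2 is Day 48 − Day 31 = 17 days.
- 20 days: 2/480 = 0.42%
- 17 days: 2/408 = 0.49%
- 14 days: 2/336 = 0.60%

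**Effect on the primary estimate.** Let r be the percent time below 54 mg/dL inside the gap and b the percent in the rest of the period. The full-period value is f·r + (1 − f)·b. The recorded value is b, because the missing time leaves the denominator as well as the numerator. The recorded value therefore differs from the full one by −f(r − b). Only one of two equal sequences has this gap on insulin, so the mean treatment difference moves by half of that.
- Extreme case, r = 100% and b = 0 in all 5 participants: 0.42/2 = 0.21, 0.49/2 = 0.25 and 0.60/2 = 0.30 points at 20, 17 and 14 days. Against the 2-point margin this is 10% to 15%.
- Illustration at 17 days, assuming b = 1% and r = 10% to 25% (neither figure is in the documents): 0.0049 × 9 / 2 = 0.02 to 0.0049 × 24 / 2 = 0.06 points understated.
- Same b, r = 0: 0.0049 × 1 / 2 = 0.0025 points overstated.
- r = b: no shift.

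If placement slipped until the gap filled all 4 hours, the extreme bound would double to 0.42 to 0.60 points.

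**The case against.** The strongest reply is that this is a checklist inconsistency with almost no statistical weight. Much of that stands. The extreme bound needs five participants below 54 mg/dL for two unbroken hours under clinic observation. If every sensor start needs a warm-up, the mid-period sensor change also costs about 2 hours in both arms, so the plan already accepts gaps of this length for the endpoint. The order may be a drafting slip, and the visit table in Appendix 5, available only by title, may settle it. None of this removes the conflict, because the section headings themselves, not just the bullet order, put placement on opposite sides of the dose.

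Several stronger readings are tempting, and the documents do not support them:

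- **That the gap favours non-inferiority.** The sign depends on whether r exceeds b, which is unknown. If saline starters also have the late placement, whatever is common to both sequences is a period effect and cancels from the treatment comparison.
- **That Visit 2 has a post-dose meter check which Visit 7 lacks.** The Visit 2 glucose values are tied to cognitive testing, which is also pre-dose. Neither visit schedules a meter value after the first dose.
- **That self-monitoring is merely optional.** Section 6.1.1 requires participants to be able and willing to check glucose as staff instruct, and to wear CGM continuously. Staff may well ask for a reading during observation; the text simply does not schedule one.
- **That the protocol requires warm-up to be complete before dosing.** Neither visit says so. Visit 2 has the sensor on first, and the test battery makes a completed warm-up likely, but this is not stated.
- **That Visit 7 dosing precedes required training.** Visit 7 does list "SipNose device teaching" after the dose, but section 5.1 says only "All subjects will receive training at start of treatment visits", without fixing the order. Participants have by then used the device throughout Period 1.

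**Conclusion.** The point holds as a minor one. Sections 7.1.2 and 7.1.7 conflict on when the CGM is placed relative to the first dose. Followed as written, at least the first 2 of 4 observed hours after the first Period 2 insulin dose have no study CGM data for about 5 of 10 participants, and the supplied text schedules no other glucose reading then.

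The effect on the primary endpoint is negligible and of unknown direction, and the non-inferiority conclusion is not threatened. What is lost is safety information on the first insulin dose and like-for-like CGM capture between periods.

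This rests on staff following section 7.1.7 literally, Period 1 sensors being worn consecutively from Day 0, equal sequences of 5, and Appendix 5 not stating a different order.

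**What to change.** Reconcile sections 7.1.2 and 7.1.7 so that CGM placement and start have the same position relative to the first dose at both visits, and so that study CGM data cover the observed hours after the first dose in both periods. Check Appendix 5 against the result. The timing of the dose itself is for the sponsor to decide.

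The cost is up to about 2 more hours at Visit 7, or about 2 hours of sensor life if the sensor is applied beforehand. At the nominal 17-day Period 2, two 10-day sensors leave 20 − 17 = 3 spare days; only a period near 20 days has none. No new device is needed.
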